	planned start of study procedures (preferably 30 days) and must have no plans to initiate systemic therapy until after study follow up is complete -OR- must be

Key Exclusion Criteria	 recorded by physician to have an active candidate lesion that is unresponsive to ongoing systemic therapy 8. Females of childbearing potential should have negative urine or serum pregnancy test within 14 days prior to initiation of study scans. 9. Demonstrate adequate organ function: determined by ANC, platelets, hemoglobin, with no gross hematuria 10. For Cohort II only: Patient is dispositioned to undergo SBRT to a bone or lung tumor 1. Clinically significant blood glucose abnormalities that preclude a satisfactory FDG PET/CT scan. 2. Previous history of external radiotherapy where prior radiotherapy fields are anticipated to overlap with the radiotherapy fields required for the present study 3. Diffuse metastatic process (leptomeningeal disease, peritoneal carcinomatosis, diffuse bone marrow involvement, etc.) 4. PET-avid structures not intended for radiation are within 2cm from target on third-party diagnostic PET/CT as assessed by investigator 5. Known psychiatric or substance abuse disorder that would interfere with conduct of the study 7. Pregnant, breast-feeding or expecting to conceive during the study 8. Patient weight exceeding the weight limit outlined per IFU. 9. For Cohort II only: Patients with pacemakers and other implantable devices who are deemed to be at high risk by the treating physician for complications secondary to radiotherapy. 10. For Cohort II only: Active inflammatory bowel disease, scleroderma, or other disorder deemed to be a risk factor for excess toxicity in the area of treatment by
Deceller	Descling Assessments within fourteen device instants the DET baseling and a set
Baseline	Baseline Assessments within fourteen days prior to the PET Imaging-only session:
Assessments	1. Demographics, medical history & physical exam
and Follow-Up Schedule	2. Complete Blood Count (CBC) 3. Comprehensive Metabolic Banel (CMB)
Schedule	 Comprehensive Metabolic Panel (CMP) ECOG performance status
	5. Blood glucose
	6. Urinalysis
	7. Pregnancy test (required for women of child-bearing potential only; within 14
	days prior to the initiation of the study scans.)
	Cohort I Follow-Up (at 72±24 hours after completion of PET Imaging-only session)
	1. AE assessment by using Common Terminology Criteria for Adverse Events
	(CTCAE) v5

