4. STUDY DESIGN

4.1 Overview and Justification for Study Design

In light of this new technology (BgRT) and its potential to improve radiotherapy dose distribution, we propose a single arm prospective study to optimize FDG dosing, assess the performance of the PET imaging subsystem for BgRT treatment planning and delivery, including its role as an interlock, and to validate the dose delivery performance of the end-to-end BgRT workflow.

As described in section 1.5, this clinical evidence is intended to supplement and enhance technical validation studies of BgRT delivery which include, but are not limited to, *in silico* simulations and physical phantom measurements. As such, the patient population selected for this investigation is meant to optimally represent the spectrum of cases, with respect to motion and radiographic environment, that a radiation oncologist may encounter in practice. As described previously, patients with lung and bone tumors are specifically selected so that diverse omnidirectional motion profiles and different tumor-to-background PET contrasts can be evaluated in the investigation.

This is a single-arm, open-label, prospective study. The study will be divided into sequential cohorts of patients with one targetable metastatic lesion in either the lungs or bone (*Figure 3*). Patients with multiple metastases can be accrued, but these investigations will focus on only one lesion per patient.

[figure not shown]

Figure 3: Study Flowchart

¹Baseline assessments and CT Simulation should be collected within two weeks prior to the RefleXion PET Imaging-only session (Visit 2). Baseline assessments and CT Simulation completed as SOC within this period do not need to be repeated for study purposes. ² within 72±24 hours after the PET Imaging-only session

³ within 72±24 hours after final FDG administration

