Immediately following the RMRS PET imaging session, subjects will be imaged again with a third-party PET/CT in the same treatment position. A second dose of FDG will not be administered for the scan immediately following the RMRS PET Imaging-only session. Sites will make every effort to minimize the time between two scans. To ensure adequate FDG activity, third-party PET scan will be initiated within 180 minutes after the FDG injection. In the unlikely event that third-party PET scan cannot be initiated within 180 minutes, third-party scan can be completed with a separate FDG injection 24 to 96 hours after the initial FDG injection in the same treatment position as per the RMRS PET scan.

Data collected during the RMRS PET Imaging-only and third-party PET/CT scans will be documented on the appropriate CRF and will include the time of FDG injection, start and end times for RMRS PET and third-party diagnostic PET/CT scans. Sites will be provided with instructions for how images should be collected and submitted to RefleXion Medical within five days of the PET Imaging-only session. AEs will be assessed by using Common Terminology Criteria for Adverse Events (CTCAE) v5 at 72±24 hours after the end of PET Imaging-only session.

After the Imaging-only PET dataset is transmitted to the RefleXion treatment planning workstation, BgRT treatment planning can be completed with dose calculation and optimization employing the BgRT

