localization ^{4,5}			
Third-party		x	
diagnostic PET/CT ^{4,5}			
AE Assessment ⁶		x	x

Table 1: Cohort I- Study Event Schedule

¹ Baseline Assessments should be completed within 14 days prior to the PET Imaging-only session

² Informed consent is not considered a baseline assessment and has no requirement to be completed within a specific time window from study visits

³Women of child-bearing potential only; within 14 days prior to the initiation of the study scans.

⁴Images should be de-identified before submitting to RefleXion Medical.

⁵ In the event that third-party PET scan cannot be initiated within 180 minutes of original FDG injection, then the third-party scan can be completed with a separate FDG injection 24 to 96 hours after the initial FDG injection. ⁶AEs to be assessed using Common Terminology Criteria for Adverse Events (CTCAE) v5

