It should be noted that cases that do not meet these criteria on the RMRS PET imaging-only session do not create a radiotherapy health risk, since the result is that the physician will not choose to use BgRT as the treatment modality. Nonetheless, the overall percent agreement and negative percent agreement will also be reported to allow for comprehensive imaging comparison with the third-party, diagnostic PET/CT.

Although calculation of the agreement endpoint will be based on the qualitative questions above (Q1 and Q2), data on target avidity and non-confounding target signal in relationship to the CT-defined, overlaid biological tracking zone (BTZ) will also be collected:

- Q3: Does the FDG-avid target fall within the BTZ?
- Q4: Do all FDG-avid OARs fall outside the BTZ?
- 6.2.4.2 As described previously, after each PET Imaging-only session on the RMRS PET, the patient undergoes sequential PET imaging on a cleared, 3rd party diagnostic PET/CT system.
- 6.2.4.3 The RMRS PET, localization kVCT, Sim CT & third-party diagnostic PET/CT images will be transferred to a workstation after the completion of imaging sessions for offline image viewing. These images will be reviewed by two separate groups of image reviewers blinded to the other device.
- 6.2.4.4 **RMRS PET review**: Three radiation oncologists will assess the RMRS PET images independently. All the readers will be trained using an identical training data set and image review software programs as detailed in the image review charter (IRC). Readers will be blinded to patient diagnosis, reader evaluations, images from the compared device (i.e. third-party diagnostic PET/CT), but not to the localization kVCT obtained on the RMRS device on the same day, Sim CT and other clinical data.
 - 6.2.4.4.1 Each reader answers the same set of questions for rating whether the patient is suitable for BgRT planning. A positive plan proceed decision requires a "yes" to both Question 1 and Question 2 above. A negative decision is any other combination of answers to the two questions.
 - 6.2.4.4.2 Individual read results will be compared to the agreement standard. A case rating will also be collected based upon agreement of two or of the three read results.

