Following the short-duration PET PreScan and long-duration PET collection, subjects will be imaged again with a third-party PET/CT in the same treatment position. A second dose of FDG will not be administered for the scan following the RMRS PET session. Sites will make every effort to minimize the time between two scans. To ensure adequate FDG activity, third-party diagnostic PET/CT scan should be initiated within 180 minutes after the FDG injection. In the unlikely event that third-party PET scan cannot be initiated within 180 minutes, third-party scan can be completed with a separate FDG injection 24 to 96 hours after the initial FDG injection in the same treatment position as the RMRS PET scan.

The time window to collect this data is within 96 hours prior to the start of the final SBRT fraction, and ideally would be done on the same day. Data collected at the last fraction of SBRT will be documented on the appropriate CRF and will include the time of FDG injection, start and end times for RMRS PET and third-party diagnostic PET/CT scans, and the results of the quantitative calculations based on the short duration PET scan. Sites will be provided with instructions for how images should be collected and submitted to RefleXion Medical within five days of the RMRS PET and third-party diagnostic PET/CT scans.

Additionally, the safety of multiple FDG administrations and toxicity rates of bladder and bone marrow will be assessed. Complete blood count, urinalysis and AEs specific to bladder and bone marrow determined by Common Terminology Criteria for Adverse Events (CTCAE) v5 will be collected at 72±24 hours after the final FDG injection.

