Unanticipated Adverse Device Effect (UADE)	Any serious adverse effect on health or safety or any life- threatening problem or death caused by, or associated with a device, if that effect, problem, or death was not previously identified in nature, severity, or degree of incidence in the investigational plan or application (including a supplementary plan or application), or any other unanticipated serious problem associated with a device that relates to the rights, safety, or welfare of subjects.	21 CFR Part 812

Underlying diseases are not reported as Adverse Events (AEs) unless there is an increase in severity or frequency during the course of the study. Death is not an adverse event but should be reflected as an outcome to another specific AE. Any AE experienced by the study subject after enrollment whether during or subsequent to the study procedures must be collected and recorded in the (e)CRF.

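### The Cohort I adverse-event visit is timed from the imaging-only session, so a subject given the fallback second FDG injection may have no contact 48-96 h after that dose

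*Combined protocol and SAP*

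**What the plan says.** Cohort I follow-up is a single AE assessment, which Attachment 1 labels as the end of study for that cohort. Its timing appears in five places, all counted from the PET imaging-only session: the synopsis, Figure 3 footnote 2 in section 4.1 ("within 72±24 hours after the PET Imaging-only session"), section 6.2.2 ("at 72±24 hours after the end of PET Imaging-only session"), the follow-up column of Table 1, and Attachment 1.

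The fallback is in sections 4.2 and 6.2.2, Table 1 footnote 5 and Attachment 1. Footnote 5 gives the trigger: "In the event that third-party PET scan cannot be initiated within 180 minutes of original FDG injection". Section 6.2.2 gives the remedy: the "third-party scan can be completed with a separate FDG injection 24 to 96 hours after the initial FDG injection in the same treatment position". None of these places restarts the follow-up clock or adds a contact.

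Section 6.2.2 describes the session as passive PET collection on the RefleXion system (RMRS) with one FDG injection, and puts the third-party scan after it. Section 6.2.4.2 gives the same order: "after each PET Imaging-only session on the RMRS PET, the patient undergoes sequential PET imaging on a cleared, 3rd party diagnostic PET/CT system".

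Cohort II allows the same second injection at its last fraction, but section 6.3.6 says its safety data "will be collected at 72±24 hours after the final FDG injection".

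**The concern.** A follow-up visit for a tracer should be counted from the last dose of that tracer. Here the clock starts at the first scan, while a second dose may come up to four days after the first. A site can follow the protocol exactly and close a subject out before the second injection, or an hour or so after it.

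Section 9.2 lists reactions that may follow FDG, including allergic reaction and glucose disturbance. Section 13.2.4 summarises exposure by number of doses and cumulative dose, and treatment-emergent AEs related to FDG; section 13.2 has the tables produced for each cohort. A two-dose Cohort I subject could therefore enter those tables with little or no scheduled observation after the second dose, and the absence of events would say less than it appears to. What is at stake is completeness of safety follow-up in a few subjects, not any efficacy or dose-finding result.

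**Working it through.** **Inputs**
- Visit window: 72±24 h, that is 72 − 24 = 48 h to 72 + 24 = 96 h after the session ends (section 6.2.2).
- Second injection, S: 24 to 96 h after the first (section 6.2.2).
- Session end, d: uptake of 45-75 min plus a 12-20 min scan (section 6.2.2) gives 57-95 min, or 0.95-1.58 h. Set-up and localization CT time is not stated. I take d = 1 to 3 h to allow for it; this is an assumption.

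**Visit time relative to the second injection**

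With time 0 at the first injection, a compliant visit falls from 48 + d to 96 + d, about 49 to 99 h. Relative to the second injection it falls from 48 + d − S to 96 + d − S.

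| Second injection, S | Earliest compliant visit | Latest compliant visit |
|---|---|---|
| 24 h | 25-27 h after it | 73-75 h after it |
| 48 h | 1-3 h after it | 49-51 h after it |
| 72 h | 21-23 h before it | 25-27 h after it |
| 96 h | 45-47 h before it | 1-3 h after it |

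The range within each cell comes from d = 1 to 3 h.

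**Where the gap opens**
- The visit can precede the second injection if S > 48 + d, that is S > 49-51 h.
- A visit at least 48 h after the second injection is possible only if 96 + d − S ≥ 48, that is S ≤ 48 + d, again 49-51 h.
- The affected part of the permitted range is 96 − (48 + d) = 48 − d = 45 to 47 h out of 96 − 24 = 72 h: 45/72 = 63% to 47/72 = 65%. This is a share of the permitted range, not a probability; the protocol gives no distribution for S.
- The whole visit window lies 48 h or more after the second injection only if 48 + d − S ≥ 48, that is S ≤ d. Since S is at least 24 h and d at most 3 h, this never happens. So a contact 48-96 h after the second dose is sometimes possible but never assured.

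**How many subjects**

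The protocol gives no fallback rate. At an assumed 5-20%, the expected number with a second injection runs from 6 × 0.05 = 0.3 to 12 × 0.20 = 2.4.

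**Under the Cohort II rule**

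The visit would be at S + 48 to S + 96 h, always 48-96 h after the second dose and 24 + 48 = 72 to 96 + 96 = 192 h after the first.

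**The case against.** The strongest reply is that the session may be read as including the third-party scan. Table 1 puts the FDG injection and the third-party PET/CT, both carrying the fallback footnote, in the imaging-only session column. Attachment 1 assigns the fallback to that same time point. The synopsis counts from completion of the session. On that reading a delayed scan delays the visit, and the gap closes. The reading is available, but it is the weaker one: section 6.2.2 ties the session to the RMRS acquisition and one injection, and sections 6.2.2 and 6.2.4.2 place the third-party scan after it. If sites can take the anchor either way, the wording still needs settling.

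A second reply is that other provisions cover the gap. Table 1 has an AE assessment in the column holding the fallback injection, the Safety Monitoring Committee reviews AEs in both cohorts, and section 9.1 says "Any AE experienced by the study subject after enrollment whether during or subsequent to the study procedures must be collected". These do reduce the risk of a missed event. None fixes a contact 48-96 h after the second dose.

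A third reply concerns materiality, and much of it stands. Cohort I has no safety endpoint and no follow-up laboratory tests. Section 10.2 expects no meaningful toxicity even from repeated FDG, and closing a subject out while a scan is outstanding would be unusual practice. It may also be said that the 48-96 h benchmark belongs to Cohort II and its safety endpoint. But Cohort I uses the same 72±24 h interval, and its single-injection subjects are in fact seen about 49-99 h after their dose; only the two-dose subjects lose that.

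**Conclusion.** The concern holds and is minor. On the operative wording, the Cohort I visit does not move with a fallback injection. A compliant visit can come 45-47 h before the second dose, and no compliant visit reaches 48 h after it once that dose is later than about 49-51 h. These figures rest on the assumed 1-3 h to session end; any value in that range gives the same conclusion. The count of about 0.3 to 2.4 subjects rests on an assumed 5-20% fallback rate and could well be at the low end, since the protocol calls the event unlikely. The RRFD decision and the Cohort I and II endpoints are unaffected.

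**What to change.** In the synopsis, Figure 3 footnote 2, section 6.2.2, Table 1 and Attachment 1, time the Cohort I follow-up at 72±24 hours after the final FDG administration, as Cohort II already does. This also removes any doubt about when the session ends for a subject who uses the fallback.

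The cost is one phrase in five places, with no new visit or test. For single-injection subjects the window moves 1-3 h earlier, which is negligible. For two-injection subjects it moves later by S − d, from 24 − 3 = 21 h to 96 − 1 = 95 h, so the latest visit is 192 h after the first injection instead of about 97-99 h.

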6.2.3 Schema for Cohort I Secondary Endpoint #1: RMRS Image Inter-Observer Agreement

6.2.3.1 The first read will occur at the clinical study site and will be the localization decision by a site Investigator as part of the planned clinical workflow. This comparison will check the decision that is made after investigator review of the RMRS PET image against an agreement standard.

- 6.2.3.1.1 The site investigator (radiation oncologist) will be presented with the RMRS PET image obtained at the PET Imaging-only session. The contours of the sim CT-defined biology-tracking zone (BTZ) will be presented on the RMRS PET image, which was acquired after anatomic registration of the sim CT with the RMRS localization kVCT. The site investigator will make a localization decision in accordance with the BgRT workflow.
- 6.2.3.1.2 The localization decision will be "Yes" if (a) the PET tumor signal is fully within the BTZ and (b) OAR and non-target PET signal(s) are outside the BTZ. Each of these two criteria will be recorded for each case. If either criterion is not met, then the localization decision will be "No". The site investigator localization decision will be logged for comparison to an agreement standard.
- 6.2.3.2 The second read will be to create the determination of an Agreement Standard to match against the localization decision of a site Investigator. This will be conducted offline at an independent center and will be done by a panel of readers.
 - 6.2.3.2.1 Three radiation oncologists will be selected. All the readers will be trained using identical training data set and image review software programs as detailed in the image review charter (IRC). Readers will be blinded to reader evaluations, patient diagnosis and other clinical data.
 - 6.2.3.2.2 The RMRS PET will be transferred to a workstation for image viewing and image registration. Readers will be presented with the RMRS PET image obtained at the Imaging-only session. The contours of the biology-tracking zone (BTZ) radiotherapy structure will be presented throughout the reading process using the same registration process as 6.2.3.1.
 - 6.2.3.2.3 Each reader makes a localization decision as "Yes" if (a) the PET tumor signal is fully within the Biology Tracking Zone (BTZ) and (b) Organ-at-risk (OAR) and non-target PET signal(s) are outside the BTZ. Each of these two criteria will be recorded. If either criterion is not met, then the localization decision will be "No".
 - 6.2.3.2.4 If reader 1 and reader 2 both rate the localization decision the same, then no third reader is required.
 - 6.2.3.2.5 If reader 1 and reader 2 are in a disagreement, then a third reader who is masked to the first two reads will perform an independent read as a tie breaker. Two agreeing out of the three read results will be selected as the Agreement Standard.
- 6.2.3.3 Inter-observer agreement between the site investigator (SI) and the agreement standard (AS) will be calculated as follows:

- 1. If both SI and AS localization decisions are "yes" then the rating should be "A"
- 2. If SI decides "yes" for localization but AS decides "no" then the rating should be "B".
- 3. If SI decides "no" for localization but AS decides "yes" then the rating should be "C".
- 4. If both SI and AS localizations decisions are "no" then the rating should be "D".
- 6.2.3.4 Based on the rating performed in above section for inter-observer agreement, an overall, positive and negative % agreement will be calculated.

Percent overall agreement = (A+D)/(A+B+C+D) {main analysis}

Percent positive agreement = A/(A+C)

Percent negative agreement = D/(D+B)

6.2.4 Schema for Cohort I Secondary Endpoint #2 - RMRS PET vs Diagnostic PET/CT Comparison:

6.2.4.1 The comparison of the PET image from the RMRS imaging-only session and the third-party diagnostic PET/CT will be conducted and descriptive statistics including positive and negative percent agreement will be provided as outlined below.

The positive percent agreement analysis seeks confirmation of RMRS findings in clinically relevant cases based on an affirmative scoring of two questions which correspond to the plan proceed decision. For the two questions, FDG-avid targets or organs are defined qualitatively as discrete structures with visually discernable FDG-PET signal above immediate background. The two questions are:

• Q1 (target avidity): Is there an FDG-avid target that correlates to the tumor location on the registered CT image?

• Q2 (confounding non-target signal): Are FDG-avid organs an adequate distance away (≥1 cm) from the FDG-avid tumor for biology-guided radiotherapy?

It should be noted that cases that do not meet these criteria on the RMRS PET imaging-only session do not create a radiotherapy health risk, since the result is that the physician will not choose to use BgRT as the treatment modality. Nonetheless, the overall percent agreement and negative percent agreement will also be reported to allow for comprehensive imaging comparison with the third-party, diagnostic PET/CT.

Although calculation of the agreement endpoint will be based on the qualitative questions above (Q1 and Q2), data on target avidity and non-confounding target signal in relationship to the CT-defined, overlaid biological tracking zone (BTZ) will also be collected:

- Q3: Does the FDG-avid target fall within the BTZ?
- Q4: Do all FDG-avid OARs fall outside the BTZ?
- 6.2.4.2 As described previously, after each PET Imaging-only session on the RMRS PET, the patient undergoes sequential PET imaging on a cleared, 3rd party diagnostic PET/CT system.
- 6.2.4.3 The RMRS PET, localization kVCT, Sim CT & third-party diagnostic PET/CT images will be transferred to a workstation after the completion of imaging sessions for offline image viewing. These images will be reviewed by two separate groups of image reviewers blinded to the other device.
- 6.2.4.4 **RMRS PET review**: Three radiation oncologists will assess the RMRS PET images independently. All the readers will be trained using an identical training data set and image review software programs as detailed in the image review charter (IRC). Readers will be blinded to patient diagnosis, reader evaluations, images from the compared device (i.e. third-party diagnostic PET/CT), but not to the localization kVCT obtained on the RMRS device on the same day, Sim CT and other clinical data.
 - 6.2.4.4.1 Each reader answers the same set of questions for rating whether the patient is suitable for BgRT planning. A positive plan proceed decision requires a "yes" to both Question 1 and Question 2 above. A negative decision is any other combination of answers to the two questions.
 - 6.2.4.4.2 Individual read results will be compared to the agreement standard. A case rating will also be collected based upon agreement of two or of the three read results.
- 6.2.4.5 Third-party Diagnostic PET/CT review: Three radiologists and/or nuclear medicine physicians with significant PET/CT experience will assess the third-party diagnostic PET/CT images independently. All the readers will be trained using an identical training data set and image review software programs as detailed in the image review charter (IRC). Readers will be blinded to patient diagnosis, reader evaluations, images from the compared device (i.e. RMRS PET and RMRS kVCT for localization) but not Sim CT and other clinical data.
 - 6.2.4.5.1 Each reader answers the same set of questions for rating whether the patient is suitable for BgRT planning. A positive decision requires a "yes" to both Question 1 and Question 2 above. A negative decision is any other combination of answers to the two questions.
 - 6.2.4.5.2 Two or more agreeing out of the three read results will be selected as the case rating. Individual read results will also be provided.
- 6.2.4.6 Based on the decisions performed in the above sections, the following table will be constructed for each RMRS PET reader individually and for the case rating collectively. Tables will be used to provide descriptive statistics for agreement as described below

Plan Proceed Decision	RMRS PET Positive	RMRS PET Negative
Diagnostic PET Positive	A	В
Diagnostic PET Negative	C	D

Percent positive agreement = A/(A+C) {Main analysis for clinically relevant cases}

Percent negative agreement = D/(B+D)

Percent overall agreement = (A+D)/(A+B+C+D)

